6.2.1. Patient Reported Outcomes

• *Mean change from baseline on Patient reported outcomes (InQoL, SF-36)(See* Protocol *Appendix 3 and Appendix 4).*

InQoL

InQoL survey consists of 45 questions within 10 sections. Four sections focus on the impact of key muscle disease symptoms (weakness, locking, pain, and fatigue), five look at the

*impact (degree and importance of impact) muscle disease has on particular areas of life, and one section asks about the positive and negative effects of treatment*⁴.

SF36

SF-36 questionnaire is a multi-purpose, short form patient-reported health survey with only 36 questions. It is a generic measure, providing an 8-scale profile of functional health as well as measuring physical and mental health. Each scale is transformed into a 0-100 scale, with a score of 0 being equivalent to maximum disability and a score of 100 being indicative of no disability⁵. It provides a measure of relative disease burden and allows differentiating the health benefits produced by various different treatments.

6.2.2. PK Endpoints

Blood samples for PK analysis of PF-0625616 will be taken according to the Schedule of Activities in the protocol. Serum PF-06252616 concentration data for the following subjects and visits will be derived.

• All subjects receiving active drug: C_{max} , and C_{trough} for all visits with PF-06252616 dosing.

6.2.3. PD Endpoints

The baseline for all pharmacodynamics endpoints is the last pre-dose value before the first day of dosing.

Graphical analysis of total GDF-8 levels as absolute and percentage of baseline will be performed. Analyses will be employed to determine the effects of dose and concentration on the GDF-8 levels over time. The GDF-8 concentrations will be summarized descriptively by treatment and time points.

6.2.4. Columbia-Suicide Severity Rating Scale (C-SSRS)

The C-SSRS will be evaluated at times specified in the Schedule of Activities of the protocol. The Baseline/Screening (Version 1/14/09) (Appendix 1 of the protocol) of the C-SSRS should be completed at the Screening Visit (Visit 1). At all study visits following the Screening Visit, the Since Last Visit (Version 1/14/09) (Appendix 2 of the protocol) of the C-SSRS should be utilized. The Since Last Visit version refers to the subject's experience since their last visit.

At Screening or Baseline, if the subject endorses a 4 or 5 on the C-SSRS ideation section or reports any suicidality behavior, then the subject is not eligible for study participation and an evaluation of suicide risk (risk assessment) must be completed.

At every visit after Screening, if the subject endorses a 4 or 5 on the C-SSRS ideation section or reports any suicidality behavior, then the subject must be discontinued as outlined in Section 6 of the protocol, Subject Withdrawal and evaluation of suicide risk (risk assessment) must be completed.

6.3. Covariates

Covariates will be summarized for the FAS and by treatment. Continuous baseline covariates will be summarized by: n, mean, median, standard deviation, min and max. Binary and factor covariates will be summarized by percent and counts.

Additional covariates including the qualitative assessment for the 4SC will be summarized over time and may be explored in the modeling of the 4SC statistical analysis.

7. HANDLING OF MISSING VALUES

Missing data for the secondary endpoints will be imputed using maximum likelihood techniques for a mixed effects model. This analysis is unbiased under the assumption of missing at random when the model assumptions hold. Subjects who lose motor functions (e.g. TUG, 2MWT) will be regarded as missing not at random. Additional imputation methods to assess the sensitivity of the analysis to missing not at random data may also be performed. A completer analysis will also be conducted as a sensitivity analysis.

Missing data for the patient reported outcome will be handled according to the guidance of the developers.

Laboratory values below the limit of quantification will be analyzed at the limit of quantification for that parameter except for PK data. For laboratory listings, the <BLQ will be used with the actual limit of quantification used in place of BLQ.

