#### 9.2.1. Analysis of Primary Endpoint

Change from baseline in FVC will be analyzed using a longitudinal mixed effects model. The baseline result, treatment, time and treatment by time interaction will be included as fixed effects in the model. Subject will be included as a random effect and the model will be fit with an unstructured covariance for the repeated measures. Additionally, non-Gaussian models may be explored in the case of non-normal data for the FVC.

Missing data will be imputed using maximum likelihood techniques for a mixed effects model. This analysis is unbiased under the assumption of missing at random when the model assumptions hold. Subjects who lose motor functions (e.g. TUG, 2MWT) will be regarded as missing not at random. Additional imputation methods to assess the sensitivity of the analysis to missing not at random data may also be performed. A completer analysis will also be conducted as a sensitivity analysis.

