8.2.2. Secondary Analyses

The secondary endpoints, change from baseline in FVC, muscle strength, timed function tests and patient reported outcome measures, will be analyzed based on the FAS using a mixed effects model with REML estimation. The change over the lead-in period, treatment, time and treatment by time interaction and will be included as fixed effects in the model. The following covariance structures and random effects will be considered: Marginal Unstructured, Marginal Variance Components, Marginal Compound Symmetry, Variance Components with Random Intercept, Unstructured with Random Intercept and Slope, Compound Symmetry with Random Intercept and Slope, Spatial Linear with Random Intercept and Slope. Choice of final model will be based on minimum AIC.

The dependent variable: change from Visit 3 at each *post-baseline interval*, i.e.: Change over post-baseline interval 1: (visit 7 –visit 3) Change over post-baseline interval 2: (visit 11-visit 3) Change over post-baseline interval 3: (Visit 15-Visit 3), for Cohort 1 only Change post-baseline interval 4: (Visit 19-Visit 3), for Cohort 1 only

Covariates are :

- Fixed effects:
 - Baseline interval change (Visit 3 Visit 2)
 - Treatment category (Dose= "5mg/kg", "5 + 40 mg/kg", "20mg/kg" or "40mg/kg")
 - o Time coded as Interval Indicator
 - Treatment category by time interaction
- Random effects:
 - Choice among Marginal Model, Random Intercept Model, and Random Intercept and Slope are selected based on the minimum AIC

Model-estimated change over each post-baseline interval with, 95% two-sided confidence intervals, will be displayed in tabular format.

For each dose level graphical displays will show model-based estimates of change in the mean functional measure from visit 3 at each visit and corresponding confidence intervals derived from the model.

Additionally a completer analysis will also be conducted as a sensitivity analysis for the missing data handling under the mixed effects modeling. The completer analysis will only

include subjects that completed all assessments at the last scheduled visit using the same longitudinal mixed effects model as the primary analysis.

Transformation of the data will be considered if model assumptions are not met.

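### Loss of motor function is declared missing not at random, but the only committed analyses assume missing at random or drop the subject

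*SAP*

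**What the plan says.** SAP section 7 sets the general rule: "Missing data for the secondary endpoints will be imputed using maximum likelihood techniques for a mixed effects model". It then gives the condition for that rule: "This analysis is unbiased under the assumption of missing at random when the model assumptions hold". The next sentence takes one group out of that condition: "Subjects who lose motor functions (e.g. TUG, 2MWT) will be regarded as missing not at random".

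No method for that group follows. SAP section 7 and protocol section 9.2.1 both leave it optional: "Additional imputation methods to assess the sensitivity of the analysis to missing not at random data may also be performed". The one firm sensitivity analysis is this: "A completer analysis will also be conducted as a sensitivity analysis".

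SAP section 8.2.2 says that the secondary endpoints, including the timed function tests, "will be analyzed based on the FAS using a mixed effects model with REML estimation". It makes no exception for a subject who can no longer do a test. The completer analysis will only "include subjects that completed all assessments at the last scheduled visit using the same longitudinal mixed effects model".

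The protocol's missing-data text sits under FVC, but protocol section 9.2.2 carries the same model over to the functional assessments.

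**The concern.** Being unable to walk for two minutes or to climb four stairs because of the disease is the worst result the test can give. It is informative, and the plan says so by calling it missing not at random. The plan then relies on an analysis that it describes as unbiased only under the opposite assumption, and backs it with a second analysis that excludes the same people.

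A subject who loses a test on treatment leaves no value. The mixed model in effect fills the gap from subjects still able to do the test and from whatever that subject did earlier. The completer analysis ignores the subject. In both, the cohort's mean change looks better than it was. Because the two analyses err in the same direction, agreement between them would not be reassuring.

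The event is foreseeable. Protocol section 8.6.1 lists loss of mobility or ambulation among events expected to be common in this population. Entry (protocol section 4.1) requires walking or running 10 m and rising from a chair, but not climbing stairs. Cohorts of 4 and 8 leave little room to absorb one such loss.

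**Working it through.** **Does any other text close the gap?**

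- SAP section 6.2 says which attempt to record when several are made. It does not say what to record when none succeeds. A time in seconds has no finite value for unable.
- SAP section 8.2.2 has no score, rank or model component for inability.
- SAP Appendix 1 plans model tables for the FAS and for completers only: TUG (14.1.1.75 and 76), 10-meter walk/run (79 and 80), 2MWT (83 and 84) and 4-stair climb (87 and 88). No table addresses data missing not at random.
- Read literally, the completer definition asks for all assessments at the last visit, so failing one test removes a subject from the completer analysis of every endpoint.

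Nothing closes it.

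**How large is the effect?** The documents give no loss rate, SD or correlation, so there is no planned figure to reproduce. What follows rests on assumptions. Change from Visit 3 is scaled to mean 0 and SD 1, with negative meaning worse. The lead-in covariate is left out.

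*Large-sample check.* Changes at Visits 7 and 11 are bivariate normal with correlation r. The Visit 11 value is lost when it falls in the worst 10% or 5%. The model predicts it by regression on Visit 7. Then

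bias in cohort mean = share lost × (implied mean of the lost − true mean of the lost).

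The true mean of the lost is −1.75 SD (worst 10%) or −2.06 SD (worst 5%). Simulation with 2,000,000 draws gives:

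| r | Worst 10% lost: implied | Bias (SD) | Worst 5% lost: implied | Bias (SD) |
|---|---|---|---|---|
| 0 | +0.20 | 0.196 | +0.11 | 0.109 |
| 0.3 | +0.07 | 0.183 | −0.05 | 0.100 |
| 0.5 | −0.18 | 0.157 | −0.35 | 0.085 |
| 0.8 | −0.89 | 0.086 | −1.17 | 0.045 |

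Example: at r = 0.8 with the worst 10% lost, 0.10 × (−0.89 + 1.75) = 0.086. The completer mean is too favourable by 0.20 SD (10% lost) or 0.11 SD (5% lost) at every r. It is never better than the mixed model.

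*One lost subject in a small cohort.* With the cohort mean and r taken as known, the implied value is r × the earlier change, or 0 if no earlier on-treatment change was observed. The shift in the cohort mean is (implied − true)/n. Take a true change of −2 to −3 SD.

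- No earlier on-treatment value, n = 8: (0 + 2)/8 = 0.25 to (0 + 3)/8 = 0.375 SD.
- No earlier on-treatment value, n = 4: 2/4 = 0.50 to 3/4 = 0.75 SD.
- Earlier change −2 SD and r = 0.8, so implied −1.6 SD, n = 8: 0.4/8 = 0.05 to 1.4/8 = 0.175 SD.
- The same, n = 4: 0.4/4 = 0.10 to 1.4/4 = 0.35 SD.

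For scale, the standard error of a cohort mean is 1/√8 = 0.35 SD or 1/√4 = 0.50 SD.

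**How much earlier information does the model have?** In Cohorts 2 and 3 the schedule has one on-treatment functional visit (Visit 7) before Visit 11. The covariance candidates begin with "Marginal Unstructured, Marginal Variance Components, Marginal Compound Symmetry" and go on to random-effects structures, chosen by minimum AIC. If variance components without random effects is chosen, earlier changes do not inform the prediction and the r = 0 row applies.

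**The case against.** The strongest reply is that a mixed model does not simply insert the average. It conditions on lead-in change, dose and time and, under most of the candidate structures, on the subject's own earlier changes. This stands. A reader might infer that each lost outcome becomes a near-average value; that holds only if function is lost before Visit 7, if variance components is selected, or if the correlation is about 0.5 or less. At 0.8 about half the decline is recovered.

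A reader might also infer that the bias always favours the drug. The documents do not support that. SAP section 8 builds its comparison group from the lead-in changes of all three cohorts. A subject who loses a test during lead-in drops out of that group and makes it look better, which works against the drug. A subject unable at Visit 3 who regains the test has no baseline, so that gain is lost too.

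Losses may be few. The natural-history study described in protocol section 1.11 found a statistically significant 12-month decline only in FVC among the functional measures. The endpoints are secondary in a safety trial with no formal sample size calculation.

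Nor would ambulation loss be invisible. Protocol section 8.6.1 has it recorded as an adverse event, efficacy data will be listed, and protocol section 7 requires the reason for an undone test to be documented. These records limit the harm to the reader's overall picture. They do not correct the modelled means or their intervals.

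**Conclusion.** The point holds. The plan classifies motor loss one way and analyses it another, and the committed sensitivity analysis cannot reveal the difference. Following the plan as written gives a biased mean whenever a test is lost through disease, so this is more than missing detail.

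The size is conditional. With the worst 10% lost, on-treatment change is too favourable by about 0.09 to 0.20 SD for correlations from 0.8 to 0, and by 0.20 SD among completers. With the worst 5% lost the figures are about 0.05 to 0.11 SD and 0.11 SD. With no losses the bias is zero. The loss rates, correlations and normal distribution are assumptions.

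It is tempting to put the distortion at 1/8 = 12.5% of baseline speed in a cohort of 8, or 1/4 = 25% in a cohort of 4. That needs the lost subject to have had average speed and everyone else to be unchanged, and the documents establish neither. If the lost subject had, say, 30% to 50% of average speed, the figures would be 3.75% to 6.25% (n = 8) or 7.5% to 12.5% (n = 4).

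**What to change.** Amend SAP sections 7 and 8.2.2, and align protocol section 9.2.1, as follows.

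1. State that disease-related inability to do a test is an observed outcome at every visit, including lead-in. Identify it from the reason that protocol section 7 already asks the investigator to document, captured as a coded field.
2. Score the 2MWT as 0 metres when the subject is unable.
3. For TUG, 10-meter walk/run and 4-stair climb, keep the planned model in seconds and make one named analysis mandatory: either speed with 0 for unable, or worst-rank. Name which before the data are analysed, and add its tables to Appendix 1.
4. Report the number unable by cohort and visit for each test.
5. Treat only absences unrelated to function as missing at random. Keep the completer analysis as supplementary.

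Moving the main timed-test models to a speed scale is not needed. It would change estimates for every subject even with no losses, and zeros in cohorts of 4 to 8 could dominate the mean, the variance and the covariance choice.

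The cost is SAP wording, a reason code and one extra analysis per timed test. A single zero can also be influential in the 2MWT model and in a speed analysis, so show those results with and without it.

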8. STATISTICAL METHODOLOGY AND STATISTICAL ANALYSES

Continuous variables will be summarized by the number (N), mean, median, standard deviation, minimum and maximum. Categorical variables will be summarized by percent and counts. All summaries will be displayed by treatment. Efficacy data will be listed, tabulated and graphically represented, as appropriate.

All analyses will be based on the full analysis set (FAS) which includes all enrolled subjects who have received at least one dose of study drug.

Below is outlining the definition of baseline for secondary endpoints :

As per Figure 1 below shows each treatment period has been divided into 16 week intervals. Endpoint is the change from the baseline to the subsequent 16th week.

A placebo group is constructed by combining the 3 cohort's running periods. Each cohort has an initial 16 week running period, they are combined together to form a placebo group which will be used as a comparison group, testing against active treatments. There will be a total of 20 subjects in the placebo group.

For cohort 1 the first comparison would be : placebo (3 cohort's running periods) vs. active treatment (1^{st} interval) which starts from the end of the running period to the end of the first 16 weeks of active treatment i.e. week 17 to week 32. The next comparison would be placebo

vs. active treatment (second interval) which starts from the end of the second 16 week active treatment i.e. week 33 to week 48. Then the next comparison would be placebo vs. active treatment (third interval) i.e. week 49 to week 64. Finally comparing placebo vs. active treatment (fourth interval) i.e. week 65 to week 80, as shown in the table 1 below.

The above rational is to be used for cohorts 2 and 3.

To conclude there will be 8 statistical tests.

Active treatment Intervals				
Cohort 1	Cohort 2	Cohort 3		
17-32	17-32	17-32		
33-48	33-48	33-48		
49-64				
65-80				

[figure not shown]

Figure 1. LGMD2i Active vs. "Placebo"

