Visit Number (Study Day Visit Window) a	1 (-125 to -112)	2 (-111 to -110)	3 (1)	4 (29 ± 3)	5 (57 ±3)	6 (85 ±3)	7 (113 ±3)	8 (141 ±3)	9 (169 ±3)	10 (197 ±3)	11 (225 ±3)	12 (337 ±3)	
Biomarkers collection m		Х					Х			Х			
Adverse event monitoring		X	Х	Х	Х	Х	X	Х	X	Х	Х	X	Х
Infusion site reaction			Х	Х	X	Х	X	Х	Х	Х	Х		Х
Concomitant medications		X	Х	X	X	Х	X	Х	Х	Х	Х	Х	Х

Abbreviations: 2MWT=Two minute walk test; 4 SC= Four stair climb, C-SSRS=Columbia Suicide Severity Rating Scale, DXA=Dual-energy x-ray absorptiometry; ECG = electrocardiogram; FSH= Follicle stimulating hormone; FVC=Forced vital capacity; FEV1 = Forced expiratory voume in 1 second; GLDH=glutamate dehydrogenase, LH-Lutenizing hormone, MIP= Mean inspiratory pressure; MEP= Mean expiratory pressure; MMT= manual muscle testing, MRI=magnetic resonance image; PD=Pharmcodynamics, PK=Pharmocokinetics, PUL=Performance of Upper Limb, TIBC=Total iron binding capacity, INQoL = Individualized Neuromuscular Disease Quality of Life, SF-36 = Short Form 36 Health Survey

- a. Assessments should be conducted on the Study Day within the visit window. Visits with MRI, DXA and functional assessments may be conducted over 2 days. The following order of testing is preferred. On the first day of assessments: an am fasting blood collection followed by fasting DXA and MRI. On the second day of assessments: the functional assessments and muscle biopsy. Whenever possible, functional testing and MRI should occur prior to biopsy. Depending on the timing of enrollment and evaluation of safety in the 20 mg/kg dose (Cohort 2), the dose escalation of Cohort 1 to 40 mg/kg may be delayed. Subjects in Cohort 1 will only receive 8 doses of the 5 mg/kg dose and not proceed to the 40 mg/kg dose until review by the SMC. In addition, depending on the timing of enrollment and evaluation of safety in the 5 mg/kg dose (Cohort 1), the Lead-In period for Cohort 2 may be extended prior to initiation of treatment phase.
- b. Medical history will include confirmation by genetic testing of the diagnosis of Limb Girdle Muscular Dystrophy (LDMG2I) as obtained from an approved laboratory. Results must confirm the presence of a biallelic alteration in the FKRP gene known or likely to be pathogenic.
- c. Enrollment can be performed once all screening results are available and eligibility is confirmed.

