## 6.2. Lead-in Period: Visit 2 (Baseline Day -111 to -110 prior to dosing on Day 1)

The following procedures and studies should be performed in the morning (before noon) of Visit 2 whenever possible

- Physical Examination, including Nose and Throat Mucosal Exam
- **Pregnancy Test**: A highly sensitive urine pregnancy test will be performed on all female subjects and must be confirmed as negative within 1 month of receiving first dose.
- Diary Cards: For collection of first day of each menstrual cycle for WOCBP.
- Contraception Review: Confirmation of use of acceptable forms of contraception
- Height: Height should be measured in the morning.
- Weight
- Vital signs: Supine blood pressure, pulse rate, respiratory rate, and oral temperature.
- Horomone Testing: LH, FSH, estrogen in WOCBP
- GLDH
- C-SSRS
- **MRI-muscle:** WB-MRI and dedicated thigh MRI will be performed for muscle quantity and quality

The following procedures should be performed in the afternoon of Visit 2 whenever possible:

- **DXA:** Whole body DXA will be performed for lean body mass.
- **Functional assessments:** Must be conducted in the following order: Respiratory function (FVC, FEV1, MIP, MEP), 4SC, 2MWT, 10-meter walk/run, TUG, strength assessment (MMT, hand-held dynamometry) and PUL.
- **Needle muscle biopsy:** Following WB-MRI and functional assessments a needle muscle biopsy of the tibialis muscle will be performed.
- PD sample collection

- **Biomarker collection:** Blood will be collected for proteomic, metabolomic, and genomic biomarker analysis
- Adverse event monitoring
- Concommitant medications

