2.1. Study Design

This is a Phase 1b/2, open-label multiple ascending dose study to evaluate the safety, tolerability, efficacy, PK and PD of PF-06252616 administered to in ambulatory participants diagnosed with LGM21. Three IV infused dose levels administered every 28 days will be investigated in a dose escalating fashion.

PF-06252616 dose levels:

- 5 mg/kg.
- 20 mg/kg.
- 40 mg/kg.

Approximately 20 eligible subjects will be consecutively assigned to 1 of 3 cohorts for approximately 96 weeks (cohort 1) or 64 weeks (cohorts 2 and 3).

Cohort 1 (n=4):

- Lead-in period (16 weeks)
- *Treatment A: PF-06252616 5 mg/kg (32 weeks)*
- Treatment B: PF-06252616 40 mg/kg (32 weeks)
- Follow-up period (16 weeks)

Cohort 2 (n=8):

- Lead-in period (16 weeks)
- Treatment: PF-06252616 20 mg/kg (32 weeks)
- Follow-up period (16 weeks)

Cohort 3 (n=8):

• Lead-in period (16 weeks)

[figure not shown]
- Treatment: PF-06252616 40 mg/kg (32 weeks)
- Follow-up period (16 weeks)

At each dose level, subjects will be followed for an initial 16-week lead-in period to establish individual change in disease progression.

The study will begin with 4 subjects being enrolled into Cohort 1. Following the lead-in period, subjects in Cohort 1 will be dosed with 5 mg/kg for a total of 32 weeks (8 doses). Cohort 2 will begin dosing at the mid dose level (20 mg/kg) once safety has been confirmed with subjects in Cohort 1 who have been treated for 16 weeks. Cohort 1 and 3 will begin dosing at the highest dose level (40 mg/kg) once safety has been confirmed with subjects in Cohort 2 who have been treated for 16 weeks.

Each dose level will be evaluated for 32 weeks (8 doses each). Cohort 1 is the only cohort who will receive 2 dose levels (5 mg/kg and 40 mg/kg) and their total treatment time will be 64 weeks.

At the conclusion of the treatment period, subjects will be followed for an additional 16 weeks to monitor for safety, PK and duration of response.

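### The SAP pools every lead-in as a 16-week untreated comparator, but the protocol lets the Cohort 2 lead-in run longer and no efficacy analysis adjusts for elapsed time

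*SAP*

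**What the plan says.** **SAP, lead-in length.** Section 2.1 states a fixed duration: "At each dose level, subjects will be followed for an initial 16-week lead-in period". Section 8 repeats it and builds the comparator from it: "Each cohort has an initial 16 week running period, they are combined together to form a placebo group". It adds: "There will be a total of 20 subjects in the placebo group".

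**SAP, treated side.** Section 8 cuts treatment into 16-week blocks: "Endpoint is the change from the baseline to the subsequent 16th week". Four blocks in Cohort 1 and two each in Cohorts 2 and 3 are compared with the pooled lead-in: "To conclude there will be 8 statistical tests".

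**SAP, fitted model.** Section 8.2.2 uses the lead-in differently. The change between Visit 2 and Visit 3, listed as "Baseline interval change", is a fixed-effect covariate. The treatment categories are the dose groups, with no placebo level. Outcomes are cumulative from Visit 3, and time is an interval indicator.

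**Protocol.** Footnote a to the Cohort 2 and 3 Schedule of Activities says that, depending on enrollment timing and the safety evaluation at 5 mg/kg, "the Lead-In period for Cohort 2 may be extended prior to initiation of treatment phase". No upper limit is given and no second Visit 2 is scheduled. Section 3.1 calls the lead-in approximately 16 weeks. Section 3.2 describes all period lengths as estimates that depend on enrollment and on safety review of the other cohorts.

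**The concern.** The lead-in is the study's only untreated observation, so the efficacy comparisons in SAP 8 rest on it. That comparison is like for like only if the untreated and treated intervals have the same length. The protocol allows one cohort, 40% of the comparator, to have a longer untreated interval, and the SAP takes the visit-to-visit change as it stands. If an extension occurs and the endpoint worsens with time, the comparator accumulates more decline than 16 weeks would produce. An inactive drug would then look somewhat protective.

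The 8.2.2 model has a related problem. Cohort 2's covariate would cover a longer period than that of Cohorts 1 and 3, and the difference coincides exactly with dose group.

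**Working it through.** **1. The plan's own figures.** Comparator size: 4 + 8 + 8 = 20. Tests: 4 + 2 + 2 = 8. Scheduled lead-in, Day -111 to Day 1: 112 days = 16.0 weeks (about 15.7 weeks at the shortest, with Visit 2 on Day -110 and no Day 0). Visit 3 to 7 (Day 1 to 113) and Visit 7 to 11 (Day 113 to 225): 112 days each. Without an extension, the lengths match.

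**2. Pooled length if all 8 Cohort 2 subjects run x weeks over.**

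(4 × 16 + 8 × (16 + x) + 8 × 16) / 20 = 16 + 0.4x weeks.

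Under linear decline the pooled change is too large by 0.4x / 16 = 2.5% per extra week.

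| Assumed x (weeks) | Pooled length (weeks) | Overstatement of 16-week decline |
|---|---|---|
| 0 | 16.0 | 0% |
| 4 | 17.6 | 10% |
| 8 | 19.2 | 20% |
| 16 | 22.4 | 40% |

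If only k of the 8 are extended, 0.4 becomes k/20. With k = 4, x = 16 gives 0.2 × 16 / 16 = 20%.

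**3. Effect on a test in SAP 8.** Take 8 treated against 20 comparator subjects, a normal approximation with independent groups, and SE = SD × √(1/20 + 1/8) = 0.418 SD. Let the true decline be d SD per 16 weeks, with no drug effect. The bias is 0.025 × x × d SD. The chance of a result favouring the drug, nominally 2.5%, is:

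| d (assumed) | x = 8 | x = 16 |
|---|---|---|
| 0 | 2.5% | 2.5% |
| 0.1 | 2.8% | 3.1% |
| 0.3 | 3.5% | 4.7% |
| 0.5 | 4.3% | 6.9% |

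The documents state neither a decline rate nor an SD, so d is an assumption.

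**4. Covariate role in SAP 8.2.2.** A simulation with no drug effect used a mean decline of 0.3 units per 16 weeks, x = 16, and Visit 7 minus Visit 3 as outcome. Cohort 2's covariate mean is then 0.3 lower than Cohort 3's.

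- Stable subject slopes dominate (slope SD 1, measurement error SD 0.2): covariate coefficient about +0.60, and the 20 versus 40 mg/kg contrast shifts by 0.60 × 0.3 = +0.18, favouring 20 mg/kg.
- Measurement error dominates (slope SD 0.3, error SD 1): coefficient about -0.40, because Visit 3 enters both covariate and outcome, and the contrast shifts by -0.12.

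With no extension both shifts are about zero.

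**5. Cumulative outcomes.** If the 32-week outcome of 8.2.2 (Visit 11 minus Visit 3) were set against the pooled lead-in, the treated interval would be the longer one, by 32 - 19.2 = 12.8 weeks at x = 8 or 32 - 22.4 = 9.6 weeks at x = 16. That works against the drug.

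**The case against.** **A reader might infer that the comparator always favours the drug. The documents do not support that.** Protocol 1.11 reports that, among the functional measures in the cited natural history study, only FVC fell significantly over 12 months. A flat endpoint gives no bias, and one that improves with practice gives the opposite bias. InQoL and SF-36 are first collected at Visit 3, so they have no lead-in change to inflate. A Cohort 1 dosing break before 40 mg/kg (protocol 3.5) would lengthen that cohort's second treated interval and, for a declining endpoint, count against the drug. All of this stands.

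**An extension may never occur.** Protocol 1.11 and 5.1 enrol Cohort 2 after the Cohort 1 safety review, which would leave little reason to extend. This stands in part, because the protocol's own timing fits poorly with strict sequencing. Section 3.3 allows 27 weeks for enrollment, yet Cohort 1 runs from Day -111 to Day 85, that is 196 days or 28 weeks, before the review. If Cohort 2 began its lead-in only then, its own Day 85 would fall near Cohort 1 Day 85 + 112 + 84 = 281, later than the Day 225 scheduled for Cohort 1's next dose level. Overlap, with a lead-in that waits on the review, is therefore plausible. The documents do not say whether it happened.

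**SAP 8.2.2 has no placebo arm.** This is correct. The arithmetic in steps 2 and 3 applies to SAP 8 only. The two sections describe different analyses, and changing the time scale does not by itself reconcile them.

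**The primary endpoints are safety endpoints.** This stands and limits the importance of the point.

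**Conclusion.** The mismatch is in the text: the SAP fixes 16 weeks in every cohort, the protocol does not, and nothing in the efficacy analysis uses elapsed time. If Cohort 2 is extended, SAP 8 would compare unequal intervals. For an endpoint with roughly linear decline, such as FVC, the pooled untreated decline is overstated by about 2.5% per extra week when all 8 subjects are extended, and by proportionally less when fewer are. The effect on a single test is modest: at x = 16 and a decline of 0.3 SD per 16 weeks, the false-positive rate in the drug's favour is 4.7% instead of 2.5%.

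The size rests on assumed values of x, decline rate and SD. The direction depends on the endpoint and, in the covariate model, cannot be predicted. The point concerns secondary endpoints only. It should be settled before analysis, but it does not threaten the trial's primary aim. FVC deserves most attention, because protocol 1.11 gives it high priority and protocol 9.2.1 builds its model on it.

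**What to change.** 1. In SAP 8 and 8.2.2, model the measurements from Visit 2 onward on actual elapsed time from visit dates, so that the lead-in contributes a rate as part of the outcome. This also handles a Cohort 1 dosing break.
2. At minimum, express the lead-in change per 16 weeks, as (Visit 3 minus Visit 2) × 16 / actual weeks, both as comparator and as covariate. Under linear decline this returns the pooled length to 16.0 weeks for any x.
3. Correct the fixed 16 weeks in SAP 2.1 and 8 to match the protocol, and tabulate actual lead-in length by cohort.
4. Add a sensitivity analysis without lead-ins longer than a limit fixed in advance. If all of Cohort 2 is extended, this leaves 20 - 8 = 12 comparator subjects.
5. State how the pooled comparison in SAP 8 and the covariate model with cumulative outcomes in 8.2.2 fit together, and what replaces the lead-in change for InQoL and SF-36.

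**Cost.** SAP wording and variables derived from visit dates already collected. Both options assume roughly linear change over the lead-in, and neither removes practice effects. Simple rescaling also shrinks measurement error and any practice gain in extended subjects (at x = 16 the factor is 16/32 = 0.5), so their variance differs from the rest. That is a reason to prefer the elapsed-time model.
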